centers in the U.S. The laboratory uses published methods and reports results with a clinically useful interpretation (70-72). Other laboratories can be used if equivalent results can be obtained. Although results from different laboratories are likely to be comparable, this has not been verified. Normal ranges are likely to be less comparable between laboratories than elevated abnormal values. It is desirable to use the same laboratory for porphyrin testing throughout the study. In general, Quest, LabCorp, ARUP or Mayo are suitable for urine and plasma porphyrin measurements. However plasma porphyrin fluorescence peak testing is only done at UTMB and ARUP. The treatment outcomes are based on criteria stated in this protocol rather than on normal ranges stated by different laboratories, which may vary considerably.

Molecular analyses to identify *UROD* mutations are provided by the Genetic Testing Laboratory at the Icahn School of Medicine at Mount Sinai in New York City.

4.B. Design. This is an open-label comparative study of the two standard treatments for PCT. Participants will be assigned to the treatment for which they are eligible, as determined by strict medical criteria as outlined in this protocol. Participants eligible and willing to receive either treatment will be randomized across sites; however the majority of participants are expected to be assigned a treatment based on their medical indications and preference. Based on many decades of clinical experience, both treatments are accepted as effective and safe. Therefore, comparing efficacy and safety will not be an objective of these standard of care treatments. Rather, the main objectives will be to compare time needed to achieve remission, as assessed by documented primary and secondary biochemical and clinical outcomes, and the durability (i.e. lack of disease recurrence) after each treatment. Since phlebotomy and low dose hydroxychloroquine are both considered accepted alternatives for treatment of PCT, costs will be either considered standard of care and charged to insurance or supported by the Porphyrias Consortium grant for those participants without insurance.

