Change of treatment. Treatment may need to be changed due to incomplete response or to side effects or intolerance of the initial treatment. Change of treatment will be a clinical decision by the investigator and the patient, and the reasons will be recorded on the CRFs. The second treatment will be monitored as part of the study with an additional set of the treatment-related CRFs in the same manner as the first treatment. Data collected after a change in treatment will be analyzed descriptively and separately from data collected during the first treatment.

Treatment of recurrences. Patients will be followed after completion of treatment in order to determine the frequency of recurrent disease, as indicated by increases in porphyrin levels with or without recurrent cutaneous manifestations. These recurrences will be monitored as part of the study. Data collected during treatment of recurrences will be analyzed descriptively and separately from data collected during the first treatment. These provisions will provide information about all treatment that is needed for this disease, since repeated courses of treatment greatly increase the impact of the disease.

4.G. Study visits during the Treatment Phase. During the Treatment Phase, participants will be scheduled to return to the study site or be contacted by the study site by telephone at 2 week intervals. A study visit can be scheduled after longer than 2 weeks based on careful review of data from the last visit. If this is contemplated, the investigative team should evaluate clinical features and laboratory results within 1 week, to be sure that a longer visit interval will not impair

capturing timely data within a documentation window. Sometimes study information can be collected by telephone, including recording of patient-reported skin manifestations, and by special arrangements study samples collected locally and shipped to the study site.

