4.I. Follow Up Phase. Determining durability of treatment after achieving a complete biochemical remission of PCT is an important objective of this study. Therefore, subjects will be observed long term during the Follow Up Phase for clinical and biochemical recurrences of PCT. This phase will begin after treatment is completed and all treatment outcomes are achieved. These visits will occur, either on site or remotely, every 3-6 months for up to 5 years, or possibly longer, depending on the availability of funding for the study. Symptoms will be monitored, and porphyrin levels measured for early detection of recurrence. Determinations on these visits will include total plasma and urinary porphyrin concentrations, plasma porphyrin neutral pH fluorescence emission peak, urinary porphyrin HPLC, ferritin and liver function tests. These samples may be obtained at the study site or elsewhere as part of standard of care. This will provide information on both clinical and subclinical biochemical recurrence after remission with both types of treatment. If a subject has a recurrence of symptoms their treatment will be followed clinically and they will continue with this follow up visit schedule.

It is important to assess both symptoms and porphyrin levels during follow up. In our experience patient reports of recurrence of skin manifestations are not always reliable, and can be discounted if evaluation at the time finds that porphyrin levels remain normal and no objective skin changes consistent with PCT are present. Conversely, biochemical recurrence with small or large increases in porphyrins can occur in the absence of symptoms. It is suspected that subclinical PCT may be especially common in patients with *UROD* mutations, but this is not well documented.

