- **4.J. Study duration and end of study.** The duration of the study including the Follow Up Phase is at least five years. It is possible that the study will be extended further depending on results and the availability of funding. Subjects will enter the study needing treatment, and require up to 24 months of treatment and observation to document achieving the treatment outcomes, followed by at least 3 years of follow-up. Therefore, the most frequent study visits will occur during the Treatment Phase and generally the first ~12 months of the study, which includes active treatment and the treatment outcome windows to document biochemical remission. Based on the interim analysis (45) it is anticipated that the first outcome (a normal plasma porphyrin concentration) will be reached within 6-7 months, on average. Other treatment outcomes should be achieved within ~12 months, although this is uncertain at present, since such observations were not part of the interim analysis.
- **4.K. Treatment outcomes and schedule of events.** A schedule of events in tabular form and a study flow diagram are shown below. This study compares time to reaching certain efficacy outcomes with the two treatments and documents durability of treatment in terms of absence of increases in porphyrins and recurrence of symptoms.

The primary efficacy outcome is achieving a normal plasma porphyrin concentration (<0.9 mcg/mL). Secondary efficacy outcomes include achieving (1) absence of a fluorescence peak in diluted plasma at neutral pH; (2) a normal level of total urinary porphyrins; (3) a normal pattern of individual porphyrins in urine (defined as total highly carboxylated porphyrins less than coproporphyrin); (4) times to achieving intermediate improvements in these porphyrin

measures, which will be defined during data analysis; (5) absence of new skin lesions for at least 3 months; and (6) effects of susceptibility factors such as hepatitis C, inherited UROD deficiency, etc. on achieving these treatment outcomes.

Durability of treatment (i.e. absence of recurrence) is recorded as beginning with the time that treatment achieves the treatment outcomes, and extends to the time of repeat documentation of a normal plasma porphyrin concentration, assuming there have been no interim recurrences of skin manifestations.

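### Section 4.K's durability rule can record a symptom-free porphyrin relapse as continued remission, against 4.F and 4.I, and 4.R does not say which definition applies

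*Combined protocol and SAP*

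**What the plan says.** The closing paragraph of 4.K sets the recording rule. It starts with "Durability of treatment (i.e. absence of recurrence) is recorded as beginning with the time that treatment achieves the treatment outcomes", and the interval then "extends to the time of repeat documentation of a normal plasma porphyrin concentration, assuming there have been no interim recurrences of skin manifestations".

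Other places describe recurrence or durability differently:

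- 4.K, opening paragraph: the study "documents durability of treatment in terms of absence of increases in porphyrins and recurrence of symptoms".
- 4.F, Treatment of recurrences: recurrent disease is "as indicated by increases in porphyrin levels with or without recurrent cutaneous manifestations".
- 4.I, Follow Up Phase: "subjects will be observed long term during the Follow Up Phase for clinical and biochemical recurrences of PCT", with the remark that "biochemical recurrence with small or large increases in porphyrins can occur in the absence of symptoms".
- Section 4, introduction (before 4.A): follow-up visits look for either biochemical or clinical signs of recurrence.

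4.B puts "the durability (i.e. lack of disease recurrence) after each treatment" among the main objectives. The synopsis lists comparison of recurrence rates as a secondary objective. 4.R plans logistic regression for the frequency of recurrence but does not define the event. 4.I schedules visits every 3-6 months for up to 5 years, with plasma and urine totals, the fluorescence peak and urine HPLC measured.

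**The concern.** The 4.K rule has one interim disqualifier, a skin recurrence, and one endpoint measurement, plasma porphyrin. A raised value between two normal plasma values does not stop the clock if the skin stays clear. An abnormal urine result or fluorescence peak does not stop it at all. Two analysts, one following 4.K and the other 4.F, could classify the same participant differently, and both could cite the protocol.

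At stake is the comparison of durability between treatments and the planned analysis of susceptibility factors for recurrence. On *UROD* carriers, 4.I says: "It is suspected that subclinical PCT may be especially common in patients with *UROD* mutations, but this is not well documented". If that suspicion is right, any undercount would be larger in one of the susceptibility groups that the study singles out as being of most clinical interest.

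**Working it through.** **No figure to reproduce.** The plan gives no recurrence rate, event count or power for durability. Its only power statement, in 4.R, concerns time to remission. The check is therefore one of wording, followed by an illustration on assumed values.

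**Step 1: start and end of the interval.** Durability starts when the treatment outcomes (plural) are achieved. Table 5 lists four: plasma level, fluorescence peak, urine total and urine pattern. 4.I likewise starts follow-up only when all are met. The closing rule looks at plasma alone. The Background account of the interim analysis reports that urine levels and patterns were often still abnormal when plasma had become normal, so plasma alone cannot stand for the other three.

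**Step 2: the two rules on the same participant, with no skin lesions in any case.**

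| Follow-up course | 4.K closing rule | 4.F wording |
|---|---|---|
| Plasma normal, raised, normal again | Durable throughout | Recurrence |
| Plasma normal, urine total raised | Durable | Recurrence |
| Plasma normal, only fluorescence peak or urine pattern abnormal | Durable | Not clearly settled; 4.I measures both |
| Plasma raised and never normal again | Stops at last normal value | Recurrence |

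The last row is not absorbed into remission, although 4.K does not say whether it counts as an event or a censored time.

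**Step 3: a dated example.** All outcomes are reached at month 12. Plasma is raised without lesions at month 24 and normal at month 36.

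- 4.K: 36 − 12 = 24 months of durability, no recurrence.
- 4.F: recurrence detected 24 − 12 = 12 months after remission. With six-monthly visits and a normal result at month 18, the onset lies between 6 and 12 months after remission.

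**Step 4: possible size, assumptions only.** Let *r* be true recurrence, *s* the symptom-free share, and *q* the share of symptom-free relapses that the rule absorbs (plasma later normal, or abnormality confined to urine or fluorescence). Then

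recorded recurrence = *r* × (1 − *s* × *q*).

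For *r* = 20%:

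| *s* | *q* = 0 | *q* = 0.5 | *q* = 1 |
|---|---|---|---|
| 25% | 20% | 17.5% | 15% |
| 50% | 20% | 15% | 10% |
| 75% | 20% | 12.5% | 5% |

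For example, 20% × (1 − 0.75 × 1) = 5%.

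**Step 5: if the share differs between groups.** With equal true recurrence of 20%, *q* = 1 and symptom-free shares of 30% and 70%, the recorded values are 20% × 0.7 = 14% and 20% × 0.3 = 6%. A difference appears where none exists. The shares are assumed.

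**The case against.** The best defence is that the closing sentence is loose wording, not a scoring rule. It glosses durability as absence of recurrence, 4.F says what recurrence is, and 4.K's opening paragraph includes porphyrin increases. Read together, a porphyrin rise ends durability. The closing sentence may mean only that time is counted to the last repeat normal plasma result, provided that no skin recurrence came between samples. It may even be a slip, with normal written for abnormal. This is a fair account of the likely intent, but it does not rescue the text. The first reading still names no biochemical event. The second still leaves out urine and fluorescence relapse.

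Three further points stand and limit the finding.

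- A reader might infer that retreated relapses would vanish from the data. They would not: 4.F and 4.Q keep retreated participants in the study and analyse that treatment separately, so the relapse is identifiable. The exposed cases are mainly untreated rises that normalise and abnormalities confined to urine or the fluorescence peak. The documents give no frequency for either.
- A reader might infer that the planned recurrence analysis is biased. That is not shown. 4.R does not say that the 4.K interval supplies its event, and an analysis on the 4.F wording would avoid this undercount.
- A reader might infer that misclassification is tied to *UROD* status. The protocol calls that link suspected and not well documented.

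**Conclusion.** The point holds as an endpoint definition that contradicts itself. The 4.K rule can record biochemical relapse as continued remission, in conflict with 4.F, 4.I, the introduction to Section 4 and its own opening paragraph, and 4.R leaves the choice open. Where the rule is used, the error goes one way: recurrence is understated and durability overstated.

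The size cannot be computed from the documents. The Background states that follow-up at the interim analysis was too short to compare recurrence rates. The range above shows what the wording allows under assumed shares, including no effect at all; it is not an estimate of bias. A larger undercount in *UROD* carriers is possible, not established.

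The primary outcome, time to a normal plasma porphyrin, is not touched. The comparison affected is described as a main objective in 4.B and as secondary in the synopsis. The conflict should be settled in the text before recurrence is analysed.

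**What to change.** Replace the closing sentence of 4.K with one event definition, used unchanged in 4.F, 4.I, 4.K and 4.R:

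- **Event.** Recurrence is the first follow-up visit at which plasma or urine porphyrins (level, urine pattern or fluorescence peak) again fail the protocol's own treatment-outcome criteria, or an objective skin recurrence, whichever comes first.
- **Limits.** State each criterion with its unit. The plasma limit is printed as <0.9 mcg/mL in 4.K but <0.9 mcg/dL in the introduction to Section 4 and in the Background, a 100-fold difference that must be reconciled. 4.K gives no number for a normal urine total, so the limit to be used should be named.
- **Time.** Durability runs from achievement of the treatment outcomes to the event, interval-censored between the last recurrence-free and the first abnormal visit. Without an event, it is censored at the last recurrence-free assessment. Later normal values or retreatment do not erase the event.
- **Reporting.** Give biochemical recurrence (plasma, urine, fluorescence) and clinical recurrence separately.
- **Sensitivity analysis.** Require the abnormality to persist at the next scheduled visit. This checks for transient rises without a confirmatory sample, which 4.I does not schedule.

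The cost is a change of protocol and analysis wording. 4.I already collects every measurement. Recorded recurrence may be somewhat higher and may include minor transient rises, which the sensitivity analysis and the separate components will show.

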This study was initially conceived as a randomized noninferiority study, with inclusion of nonrandomized participants to be treated and followed in a substudy. But as described above, an interim analysis found that more than half the participants were either not medically eligible for both treatments or preferred to choose their treatment, and therefore were not eligible for randomization (45). The results found no major demographic or clinical differences between randomized and nonrandomized participants, and treatment responses were also similar. For reasons noted above, the study will continue with inclusion of all treatment-eligible participants as a more pragmatic study relevant to clinical practice, with assignment to treatment based on uniform criteria and randomization only of participants eligible for both treatments, to avoid unnecessary bias. A descriptive approach to data analysis will be employed, with clinically relevant comparisons of the two treatments. A larger number of subjects will allow assessment of effects of susceptibility factors on treatment response and durability.

Study visits are scheduled at 2-4 week intervals to document achieving a target ferritin concentration in subjects treated by phlebotomy, and for both treatments achieving a normal plasma porphyrin concentration. Visits may be less frequent than 2-4 weeks early in the course of treatment if, for example, during a course of phlebotomies the serum ferritin is still well above the target concentration, or if after phlebotomies are complete or during hydroxychloroquine treatment the plasma porphyrin concentrations are still quite high and not yet approaching normal.

Once a normal plasma porphyrin concentration is achieved visits will then be scheduled at 4-8 week intervals to document achieving the additional treatment outcomes and complete remission of PCT. Less frequent visits may be scheduled if these outcomes are not yet approaching normal, although the time course of improvements in these outcome parameters can be difficult to predict. The expected order of achieving these outcomes with each treatment is as follows:

- 1. Phlebotomy only: Target ferritin (<20 ng/mL) expected ~2 weeks after the last phlebotomy. (This requirement can also be met by a ferritin of 25 ng/mL on the same day as the last phlebotomy.)
- 2. Normal plasma porphyrin concentration
- 3. Absence of a fluorescence peak in plasma at neutral pH
- 4. Normal urine total porphyrins

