Liver ultrasound and biopsy will be recommended to participants based on clinical indications per the investigator, these tests will not be done solely for the study. If completed at an outside institution records will be obtained. Tissue will be examined microscopically, and iron content will be measured if possible. Evaluation of liver histology is not required for this study because the results are usually not essential for diagnosis or classification of PCT participants, identifying risk factors, or deciding on treatment options. However, liver biopsy is the best means of assessing liver iron concentration, and is often recommended for assessing the degree of pretreatment damage to the liver associated with hepatitis C, alcohol, steatosis, etc. Results of liver biopsy, when available, will be recorded on the CRFs and tabulated and analyzed with other clinical information that pertains to PCT.

Treatment assignment. Before assigning treatment, subjects will be evaluated for the contraindications to treatment with hydroxychloroquine and phlebotomy listed in Table 3 and 4.

If one of these treatments is contraindicated, the reason(s) will be recorded, and the subject will be assigned to the other treatment. Participants eligible for both will be assigned by randomization.

Table 3. Contraindications to treatment with hydroxychloroquine.

- 1. Unwillingness to consider this form of treatment
- 2. Lactating women
- 3. Psoriasis
- 4. Significant retinal disease
- 5. Glucose-6-phosphate dehydrogenase deficiency
- Recent and continued heavy use of alcohol (defined as 28 or more drinks per week)
- 7. Recent and continued use of hepatotoxic drugs such as acetaminophen, isoniazid or valproic acid
- Marked abnormalities in liver function tests at baseline, such as serum bilirubin >3mg/dL, serum alanine aminotransferase >200 U/L, or prothrombin time >16 seconds (or INR >1.4)
- 9. Advanced renal disease, with serum creatinine >3 mg/dL
- 10. Poor tolerance or poor response to this treatment in the past
- 11. HFE genotypes C282Y/C282Y or C282Y/H63D and serum ferritin above the normal range (>336 ng/mL)
- 12. Substantial iron overload, with serum ferritin >500 ng/mL, in the absence of these *HFE* genotypes
- 13. Marked iron overload (3+ or 4+) on liver biopsy, if available

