4.L. Safety. Safety parameters are based on known side effects of both treatments and include suggestions of the UTMB IRB and the FDA CDER. Participants will be evaluated at the beginning of the study to ensure that they meet the entry criteria and are informed about risks and precautions. They will then be monitored at study visits for assessment of safety. Close monitoring of hemoglobin or hematocrit may occur as a part of standard treatment by phlebotomy. This is not the case for hydroxychloroquine, because initiation of treatment in clinical practice requires only one visit to prescribe the drug, and continued visits are not needed to administer treatment. Therefore, safety monitoring will be as good or better than in clinical practice.

1. History and physical examination

History and physical examination (including height and weight) will be performed at the beginning and end of the study. Results will be recorded on CRFs.

Schedule of Events

| | Baseline (Day -60 to Day -1) | Treatment Period (including all treatment outcomes) | Follow Up Period (to monitor for recurrence) |
|---|------------------------------------|---|--|
| Visit frequency | One visit or as needed | Every 2-4 weeks until plasma porphyrin concentration normal, then every 4-8 weeks | Every 3-6 months |
| Medical History and physical examination | Х | | Annually & End of study |
| Documentation of PCT & porphyrin testing- urine total porphyrins, plasma total porphyrins*, erythrocyte protoporphyrin, UROD mutation testing, erythrocyte UROD, urine ALA & PBG, fecal porphyrins (optional) | х | | |
| Lab assessment for susceptibility factors- serum anti- HCV (with follow up HCV RNA if positive), serum anti- HIV, HFE mutation testing | X | | |
| Screening Lab tests- serum ferritin, complete metabolic panel%, CBC with Diff, hemoglobin A1C, Erythrocyte glucose-6-phosphate dehydrogenase screening, PT, aPTT, serum iron & TIBC | Х | | |
| Alcohol & Tobacco Use Questionnaires | X | | |
| History of Estrogen Use (type, dose, duration, how recent) | Х | | |
| PCT Symptom Assessment | Х | Х | Х |

| Liver ultrasound and/or liver biopsy (if clinically indicated) | Х | | |
|---|---|----------|---|
| Ophthalmologic Evaluation (only for HCQ participants) | Х | Annually | |
| Plasma and urine (24 hour or spot sample) total porphyrins, quantified & plasma porphyrins fluorescent peak# | | X | X |
| Urine pregnancy test | Х | X | |

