| Follow Up Lab tests- Hepatic Function Panel with reflex to PT and aPTT if abnormal, HCV RNA if positive at baseline | | х | х |
| Serum Ferritin [®] (follow up needed only for phlebotomy participants) | Х | х | Х |
| Dispense HCQ or begin phlebotomies | | X | |
| HCQ twice weekly or ~biweekly phlebotomies\$ | | Х | |
| Investigator review of labs to determine next visit | | PRN | X |
| Collection of urine for research testing | Х | X | X |

[figure not shown]
#Plasma porphyrin scan at neutral pH can be done at UTMB or ARUP, urine and plasma porphyrin measurements can be done at UTMB, ARUP, Mayo, Quest or LabCorp. During treatment phase once plasma levels drop to less than ~5 mcg/dL the test should be repeated biweekly

@ Serum ferritin should be done biweekly once the level drops below 60 ng/mL, until the target of ≤20 ng/mL is reached

[%]Complete Metabolic Panel should include- sodium, potassium, chloride, carbon dioxide, blood urea nitrogen, creatinine, total protein, albumin, total bilirubin, glutamic oxaloacetic transaminase [aspartate aminotransferase], serum glutamic pyruvic transaminase [alanine aminotransferase], glucose, uric acid, calcium, and phosphorous

^{\$} For participants on HCQ the coordinator will need to complete compliance forms monthly. For participants on phlebotomy the phlebotomy visit sheet will need to completed at every phlebotomy visit

Study flow diagram:

2. Laboratory evaluations

The tests listed below are required to assess safety of treatment or detect concurrent conditions that might affect treatment indications. Examples of the latter include advanced liver disease, chronic renal disease and myelofibrosis and other bone marrow disorders. The serum pregnancy test is needed in women of child-bearing potential to exclude pregnancy, because this is a reason for exclusion at the start of the study or for stopping treatment during the study.

- a. The following will be measured by the hospital clinical laboratory.
 - i) Tests done at baseline
 - Erythrocyte glucose-6-phosphate dehydrogenase activity

- Prothrombin time
- Partial thromboplastin time
- Total protein
- Albumin
- Total bilirubin
- Aspartate aminotransferase (glutamic oxaloacetic transaminase)
- Alanine aminotransferase (glutamic pyruvic transaminase)
- Iron
- Iron binding capacity
- Transferrin percent saturation
- Ferritin

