- Complete blood cell count (to include hemoglobin, hematocrit, red blood cell count, red blood cell indices, white blood cell count, differential white blood cell count and platelet count)

- Sodium
- Potassium
- Chloride
- Carbon dioxide
- Blood urea nitrogen
- Creatinine
- Glucose
- ii) Tests done at subsequent visits
 - Repeat baseline tests that were abnormal, or are clinically indicated
 - Total bilirubin
 - Aspartate aminotransferase (glutamic oxaloacetic transaminase)
 - Alanine aminotransferase (glutamic pyruvic transaminase)
 - Iron
 - Iron binding capacity
 - Transferrin percent saturation
 - Ferritin
 - Prothrombin time and partial thromboplastin time if liver function tests are abnormal

A urine or serum pregnancy test will be done at baseline and every 2 months until the end of treatment in premenopausal females; pregnancy is a reason for exclusion at any time during the study.

Hydroxychloroquine will be discontinued if there is worsening of liver disease, as determined by a rise in alanine aminotransferase to >300 U/L, or a two-fold increase from baseline in either total bilirubin or prothrombin time. Participants will also be monitored at each visit for signs or symptoms of worsening liver disease. Phlebotomy will be discontinued if participants are unable to tolerate this treatment at least monthly. Randomized patients discontinued from either treatment may be treated with the alternative method, since an objective of this pragmatic study is to achieve remission in all patients.

3. Ophthalmologic examinations will be done in all participants treated with hydroxychloroquine at the beginning and end of treatment. This is consistent with the recommendations of the American Academy of Ophthalmology as updated in 2011 (Table 7) [78]. Because retinal damage from 4-aminoquinolines is very rare (especially with hydroxychloroquine), it is not expected that ocular effects will be observed in this small study

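### The hydroxychloroquine stopping rule in 4.L sets no minimum bilirubin level, so a doubling that stays within the normal range forces a stop

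*Combined protocol and SAP*

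**What the plan says.** Section 4.L (Safety, laboratory evaluations) states: "Hydroxychloroquine will be discontinued if there is worsening of liver disease". It then defines worsening by laboratory results: ALT above 300 U/L, or "a two-fold increase from baseline in either total bilirubin or prothrombin time". The ALT limb has an absolute level. The bilirubin limb has none and does not refer to a normal range.

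The Schedule of Events describes the baseline period as "One visit or as needed" and lists for the treatment period a "Hepatic Function Panel with reflex to PT and aPTT if abnormal". Section 4.L also names total bilirubin among the tests at later visits. Section 4 adds: "Visits may be less frequent than 2-4 weeks early in the course of treatment".

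The only absolute bilirubin level in the protocol is in Table 3, as a contraindication to starting the drug: "Marked abnormalities in liver function tests at baseline, such as serum bilirubin >3mg/dL".

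On what follows a stop, section 4.F says: "Change of treatment will be a clinical decision by the investigator and the patient". It continues: "Data collected after a change in treatment will be analyzed descriptively and separately from data collected during the first treatment". Section 4.R keeps everyone who starts treatment in the analysis and expects the hydroxychloroquine group to be the smaller one.

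**The concern.** The wording leaves no room for judgement. The laboratory limits define worsening, so a participant whose bilirubin doubles from a low normal value must stop even if the result is unremarkable. Baseline will often be a single reading. One low reading then becomes the denominator for every later comparison, and repeated testing adds further chances of a trigger. Section 5.A also calls slight, transient rises in liver tests normal and expected on this regimen.

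A needless stop interrupts effective therapy. If it comes before remission and a switch follows, later data leave the first-treatment analysis. It may also be recorded as liver worsening in a study that assesses tolerability. Section 4.L has no matching liver rule for phlebotomy, so the effect falls on one group.

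**Working it through.** **Text check.** Every statement on bilirubin, liver tests and discontinuation that was available was compared with the rule.
- 4.H adds reasons to stop, and neither it nor 4.Q limits this rule.
- Table 3 applies before treatment starts.
- The 4.L instruction to repeat tests concerns those abnormal at baseline or clinically indicated. It sets no level for an on-treatment rise.
- A part of 4.F just before the change-of-treatment paragraph was not available. It lies outside 4.L.

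The plan states no error rate for the rule, so there is no figure to reproduce.

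**Arithmetic of the rule.** It is met at 2 × baseline. The doubled value is still normal whenever baseline ≤ ULN/2. For an assumed upper limit (ULN) of 1.0, 1.2 or 1.3 mg/dL, that means a baseline up to 0.5, 0.6 or 0.65 mg/dL. A doubling from 1.5 mg/dL or less ends at or below 2 × 1.5 = 3 mg/dL, the Table 3 level.

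**False triggers: assumptions not in the documents.** Stable true bilirubin of 0.4-0.8 mg/dL; log-normal within-person variation with CV 10-25%; one baseline reading; ULN 1.2 mg/dL; no drug effect on bilirubin. The 4-14 tests cover about 6.5 months: 14 is a test every 2 weeks, 7 every 4 weeks, and 4 allows for sparser early visits.

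For one test, P = 1 − Φ(ln 2 / (s√2)), with s = √ln(1 + CV²). This gives 0.05% at CV 15%, 0.67% at CV 20% and 2.3% at CV 25%.

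For at least one trigger over several tests, simulation (200,000 participants per cell, results rounded to 0.1 mg/dL) gives, for true levels 0.4 / 0.6 / 0.8 mg/dL:

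| CV | 4 tests | 7 tests | 14 tests |
|---|---|---|---|
| 15% | 1.3 / 0.8 / 0.5% | 2.1 / 1.2 / 0.8% | 3.9 / 2.1 / 1.4% |
| 20% | 5.8 / 4.3 / 3.7% | 8.8 / 6.7 / 5.5% | 14.6 / 9.9 / 8.7% |
| 25% | 12.6 / 10.6 / 9.6% | 17.8 / 15.0 / 13.8% | 26.0 / 21.6 / 20.3% |

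At CV 10% every cell is at most 0.1%. Without rounding, the ranges over 4-14 tests are 0.2-0.6%, 2-6% and 7-17% at CV 15, 20 and 25%.

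**Adding only the floor (value also above ULN).** The worst case, CV 25% and 14 tests, falls to at most about 1.5% at 0.4-0.6 mg/dL and about 12% at 0.8 mg/dL. These two ceilings treat the true level as the mean of a participant's readings. Treating it as the median, as in the table, gives about 2% and 13%. At 1.0 mg/dL there is little or no gain, because twice most baseline readings already exceeds 1.2.

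**Detection of a true, sustained two-fold rise over 7 tests.** Without rounding, the baseline reading doubled and the 7 later readings are exchangeable. The chance that at least one later reading reaches twice baseline is therefore 7/8 = 87.5% at any CV. With rounding it is about 88-90% from 0.8 mg/dL or above, with or without the floor. From 0.6 mg/dL it is about 88% with the floor against 90% now. A doubling that ends within the normal range is largely no longer caught, which is the purpose of the floor.

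**The case against.** The strongest defence is that this is a deliberately sensitive rule. Section 4.L says its safety parameters include suggestions from an IRB and the FDA. Section 2 reports liver damage in virtually all untreated patients and acute hepatic injury at larger doses of this drug class, and an effective alternative exists. That supports having a liver rule. It does not explain a bilirubin limb that normal results can meet.

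The frequency argument has more force. CV, true level, rounding and ULN are all assumed, and the answer runs from about 0% to 26%. Bilirubin may also often be higher than 0.4-0.8 mg/dL, since section 4.E says liver-test abnormalities are typical, and then the floor helps less. The 14-test column is a ceiling: 4.G allows some contacts by telephone, and the hepatic panel has no stated frequency. The interim results reported in section 2 mention no bilirubin stops.

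Four stronger readings are tempting, and the documents do not support them.
- A reader might infer that the lack of a confirming sample is itself a defect. Requiring one before stopping is a real safety trade-off: with both the floor and a repeat, detection of a true rise from 0.8 to 1.6 mg/dL over 7 tests drops from about 90% to 72-74%.
- A reader might infer that Table 3 contradicts 4.L. An entry level and an on-treatment change rule can properly differ, so the 3 mg/dL figure only gives a sense of scale.
- A reader might infer that every stop leads to a switch and a lost outcome. Sections 4.F, 4.H and 4.L leave switching to judgement. Section 4.Q does say that participants who fail or develop contraindications will be switched, but it does not say that a bilirubin stop is one. Nothing in 4.L forbids a recheck or restart.
- A reader might infer that a material number of participants will be lost. No such count can be derived.

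**Conclusion.** The point holds as a minor one. On its wording, 4.L requires hydroxychloroquine to stop for a bilirubin doubling at any level, including wholly within the normal range, and no section that could be checked adds a minimum. That conclusion rests on the text alone. The frequency of false stops is illustrative and turns mainly on the CV: negligible at 10%, a few per cent or less at 15%, and possibly 10-26% at 25% with rounded results. The floor removes most of these at low true levels, about half or less at 0.8 mg/dL in the least favourable cells, and almost none at 1.0 mg/dL. The loss of first-treatment data is conditional on a stop before remission followed by a switch.

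**What to change.** Change the bilirubin limb of 4.L to: total bilirubin at least twice baseline and above the laboratory's upper limit of normal. Stop on the first such result, as now. Leave the ALT limb, the prothrombin-time limb and the monitoring for signs and symptoms unchanged. Do not require a repeat sample before stopping.

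The cost is one sentence and no extra blood tests. Because IRB and FDA suggestions shaped these parameters, the amendment should go to both. The downside is that a true doubling that stays within the normal range will no longer stop the drug. The change helps only participants still on, or yet to start, hydroxychloroquine.
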